2.2 Secondary Objectives

1. To establish the acceptability and reproducibility of using indirect calorimetry to measure energy expenditure as compared to use of standard predictive energy equations.
2. To determine whether metabolic parameters of REE or RQ are potential surrogate biomarkers to predict weight loss.

3 Study design

Type of study: Randomized-controlled trial

Primary endpoint

Reduction in body weight from baseline to end-of treatment (24 weeks)

4. Study population

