4.3 Exclusion criteria

- Taking weight loss medication within 12 weeks prior to randomisation
- Previous or planned bariatric surgery
- History of Type 1, Type 2 diabetes mellitus, DKA or diabetes secondary to pancreatitis
- Has a HbA1c of $\geq 6.5\%$ (or ≥ 48 mmol/mol)
- History of obesity with a known secondary cause (e.g. Cushing's disease / syndrome)
- Oral corticosteroid use (except in the short term use of a 7-10 day course)
- Ongoing, inadequately controlled thyroid disorder defined as thyroid-stimulating hormone >6 mIU/litre or <0.4 mIU/litre
- History of malignancy within 3 years before screening (or diagnosis of malignancy within this period)
- eGFR ≤ 30 ml/min/1.73m² on serum testing
- Alanine aminotransferase level is >2.0 times the upper limit of normal or total bilirubin is >1.5 times the upper limit of normal at screening
- Other major illness likely to preclude participation in the trial
- History of glucagonoma

- An MI, unstable angina, revascularization procedure (stent or bypass graft surgery) or cerebrovascular accident within 12 weeks before screening
- Heart Failure NYHA Class III-IV
- End-stage Chronic Obstructive Pulmonary Disease (COPD)

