4.5 Withdrawal criteria

Participants may withdraw consent from the study before study completion if they decide to do so, at any time and for any reason. If a participant decides to withdraw from the study, this will be recorded in the study records. They will be sent a letter thanking them for their participation, and informing them that the data collected up to the time point they withdrew will be included in the study analysis and that they will not be contacted again with regards to this study. They will not be asked to attend further visits. Furthermore, we will emphasise that their standard care will not be affected by their withdrawal from this study and that they will return to standard care.

Participants will be withdrawn from this study by the research team as agreed by the PI if:

- They are diagnosed with a terminal illness
- The PI, sponsor or study clinician deem it unsafe for continuation in the study for medical, safety, regulatory or other reasons consistent with applicable laws, regulations, or Good Clinical Practice (GCP)
- They are considered to be lost to follow-up as deemed by the clinician.
- Loss of capacity during participation in research
- Treatment with medications which the PI determines to require permanent withdrawal from the study (e.g. systemic corticosteroids)

[figure not shown]
- Female participants with a positive pregnancy test

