5.3 Randomisation

During the baseline visit (week 0), randomisation will be conducted through a validated online system provided through the Clinical Trials Unit. Eligible participants will be randomly assigned in a 1:1 ratio to:

- 1) SC (control group) – standard care including diet, exercise and behaviour modification therapy, but energy expenditure information is **withheld** from both the clinicians and participants until the final visit.
- 2) ECAL (intervention group) – in addition to diet, exercise and behaviour modification therapy, participants will receive verbal feedback on nutrition energy goal based on their REE measurement. The REE information will then be used to guide dietary and lifestyle recommendations. The measured energy information will be presented to the participant as a layperson summary at respective visits. This includes RMR, RQ and any other metabolic measurements obtained from IC tests.

Participants will be informed of their randomization assignment during the Baseline Visit. A letter will be sent to the participant's GP notifying them of their patient's participation in the study.

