9.2 Consent

Consent to enter the study must be sought from each participant only after a full explanation has been given, an information leaflet offered, and time allowed for consideration. Signed participant consent should be obtained. The right of the participant to refuse to participate without giving reasons must be respected. After the participant has entered the study the clinician remains free to give alternative treatment to that specified in the protocol at any stage if he/she feels it is in the participant's best interest, but the reasons for doing so should be recorded. In these cases, the participants remain within the study for the purposes of follow-up and data analysis. All participants are free to withdraw at any time from the protocol treatment without giving reasons and without prejudicing further treatment.

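### Section 4.5 takes participants out of the study, not just off the intervention, for medication the PI judges to require it, with no provision to measure the week-24 weight

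*Protocol*

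**What the plan says.** The withdrawal list in protocol section 4.5 opens with "Participants will be withdrawn from this study by the research team as agreed by the PI if", so what follows is an instruction to remove the participant from the study. One bullet is "Treatment with medications which the PI determines to require permanent withdrawal from the study (e.g. systemic corticosteroids"). It gives no drug list, dose or duration. A separate bullet covers safety: "The PI, sponsor or study clinician deem it unsafe for continuation in the study for medical, safety, regulatory or other reasons".

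Section 4.5 describes what happens after withdrawal only for participants who decide to leave: their data to that point are used and they are not asked to further visits. It has no corresponding text for participants removed by the team.

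Section 9.2 takes a different approach. Where the clinician gives treatment other than that specified, "In these cases, the participants remain within the study for the purposes of follow-up and data analysis". The section then refers to leaving the treatment, not the study: "All participants are free to withdraw at any time from the protocol treatment without giving reasons and without prejudicing further treatment".

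The primary endpoint in section 3 is "Reduction in body weight from baseline to end-of treatment (24 weeks"). On masking, section 5.3 states "Participants will be informed of their randomization assignment during the Baseline Visit". Section 5.2 withholds the calorimetry report from participants and treating clinicians in the standard care arm. It says nothing about masking the PI.

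**The concern.** A participant who starts a systemic corticosteroid after randomisation is to be taken out of the study if the PI so judges. Corticosteroids act on weight, which is the primary endpoint. Because the arm is known and no masking of the PI is stated, the judgement may be made with the arm, and possibly the weight course, in view.

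If such removals differ between arms in number or kind, the participants left at week 24 no longer form the randomised comparison. A statistical analysis plan can choose how to handle a missing weight, but it cannot recover one that was never measured. Who stays in follow-up is fixed by the protocol, so this is the document to correct.

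**Working it through.** **The two clauses side by side**

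| | Section 4.5, medication bullet | Section 9.2 |
|---|---|---|
| Trigger | a medication the PI judges to require withdrawal | the clinician gives treatment other than that in the protocol |
| Consequence | permanent withdrawal from the study | stays in follow-up and analysis |
| Week-24 weight | no provision | implied by continued follow-up |

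A drug started by the study clinician in place of protocol treatment can meet both triggers, with opposite consequences. A corticosteroid prescribed elsewhere for an unrelated illness may meet only the first. The overlap is therefore partial, and no text says which clause governs within it.

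**The plan's own sample size (section 4.4)**

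Inputs: SD 4.88 kg, difference 3 kg, power 80%. Section 6.2 gives the 0.05 level; two-sided is assumed.

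n per arm = 2 × (1.960 + 0.842)² × 4.88² / 3² = 41.5, rounded up to 42. Total 84, and 84 / 0.80 = 105. The stated figures reproduce. With 42 per arm, the two-sided t-test has 79.5% power.

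**Scale of a one-sided loss**

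Assumptions, none from the documents: k participants of 42 are lost from one arm and not matched in the other, and their week-24 weight change would have differed from the rest of that arm by one SD.

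- Shift in the treatment difference = k × 4.88 / 42, which is 0.116 kg for k = 1 and 0.465 kg for k = 4.
- Relative to the 3 kg target: 0.116 / 3 = 3.9% and 0.465 / 3 = 15.5%.
- Standard error = 4.88 × √(2/42) = 1.065 kg, so the shift is 0.11 to 0.44 standard errors.
- t-test with 42 against 42 − k and no true difference: the rejection rate is 5.13% (k = 1) or 7.05% (k = 4) instead of 5%.
- If the shift works against the ECAL arm, the detectable difference becomes 3 − 0.116 or 3 − 0.465 kg, and power is 75.8% or 63.0%.

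A wider range comes from shift = f × D, with a share f removed from one arm who differ by D kg. For f of 2% to 10% and D of 3 to 8 kg, the shift runs from 0.02 × 3 = 0.06 kg to 0.10 × 8 = 0.8 kg, or 2% to 27% of 3 kg.

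**Losses alike in both arms**

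The shift cancels. Power for 3 kg is 77.5% at 40 per arm and 75.3% at 38.

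**Base of these figures**

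The 42 per arm is what remains after the 20% attrition allowance (105 − 84 = 21 participants). The power figures therefore describe losses beyond that allowance.

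**The case against.** Several objections have weight.

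- **A reader might infer that 4.5 and 9.2 flatly contradict each other.** The documents do not support that. Section 9.2 concerns an alternative to the protocol treatment, which is diet, exercise and behaviour therapy. A corticosteroid for an intercurrent illness need not be such an alternative, and 4.5 can be read as a specific exception. This stands; what remains is a difference of approach where the triggers overlap.
- **A reader might infer that the bullet exists for reasons other than safety, because safety has its own bullet.** That does not follow. Terminal illness and pregnancy are also listed separately, so the bullets overlap.
- **A reader might infer that weight-loss drugs fall under the bullet.** Section 4.3 bars them only before randomisation ("Taking weight loss medication within 12 weeks prior to randomisation"), and 4.5 does not name them. The PI could include them, but the text does not say so.
- **A reader might infer that the week-24 weight is certainly lost.** The rule against further visits is written only for participants who choose to leave. Loss after removal by the team is likely but not stated.
- **No mechanism for arm-dependence is shown.** Nothing in the documents suggests that calorimetry feedback changes who needs corticosteroids, and the PI's part in visits is not described. Imbalance is thus a risk, not an expectation.
- **The attrition allowance absorbs some losses.** This holds for precision. The allowance gives no protection against selective loss.

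None of this removes the core point: the bullet orders withdrawal from the study on a post-randomisation judgement, in an open trial, and does not secure the endpoint.

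**Conclusion.** The point holds as a weakness in how withdrawal is defined. Section 4.5 joins a reason to stop or change the intervention to removal from the study, and so leaves collection of the primary endpoint to a judgement not stated to be masked. Section 9.2 shows that the protocol already accepts retention in a neighbouring situation.

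The size cannot be derived from the documents, which give neither the frequency nor the effect of such medication. It is probably modest. The shifts and error rates above depend on assumed one-sided losses of an assumed kind and indicate scale only; the 63.0% power figure needs four losses beyond the allowance, all in one arm, all one SD off, and all acting against ECAL. The finding does not question the planned sample size. It is best classed as a cheap improvement.

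**What to change.** Replace the medication bullet in 4.5 with text such as:

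> Starting a medication after randomisation, including a systemic corticosteroid, is not in itself a reason to leave the study. The PI may stop or modify the protocol dietary advice. Unless consent is withdrawn or the safety criterion applies, the participant stays in follow-up, the medication and its start date are recorded, and the week-24 weight is measured and analysed in the randomised arm.

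Leave consent withdrawal and the safety bullet as they are.

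The cost is one bullet and a medication record, with no extra visit because week 24 is already scheduled for everyone. The downside is that the estimate then includes the effect of such drug use, and unequal use between arms becomes part of the measured difference. A sensitivity analysis that excludes weights taken after the drug was started can show how far this matters. The other discretionary routes in 4.5, such as the clinician's judgement that a participant is lost to follow-up, are not changed by this edit.

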4.6 Prohibitions and Restrictions

Potential participants must be willing and able to adhere to the following prohibitions and restrictions during the study to be eligible for participation:

- Willing to have an overnight fast of at least 8 hours or greater before the IC measurement.
- Willing to avoid stimulants and stressors such as caffeine, nicotine, and tobacco for at least 8 hours prior to the test. The allowed beverages are water only for the duration of pre-testing phase.
- Willing to avoid strenuous physical activity for 12 hours prior to the measurement.

Figure 1: Recruitment, consent, and randomisation of trial participants.

5. Experimental protocol

5.1 Screening Visit

The Screening Visit is performed at least one day and up to 2 weeks prior to the Randomisation Visit.

Patients will attend an appointment with a healthcare professional at the study site. The healthcare professional will confirm and check their eligibility to participate and explain in detail what the study involves and allow for any questions regarding the trial. Full written informed consent to participate will then be taken. The person obtaining consent will also have been named in the delegation log of staff as undertaking this duty and approved as study personnel by the relevant governance procedures.

After consent has been obtained, a member of the team will perform measurement of anthropometrics (height, weight, waist circumference, blood pressure and pulse rate) for all the patients in line with study Standard Operating Procedures (SOPs) and arrange for standard laboratory testing (listed blood tests – HbA1c, FBC, U+E, Lipids, LFTs, TFTs) and urine pregnancy test (female participants of childbearing potential only).

Each participant will have a copy of the consent form and patient information leaflet. A copy will be placed in their hospital medical records and the original copy held in the site Masterfile.

5.2 Baseline visit & Randomisation

Eligible participants will be able to proceed to the Baseline Visit (Week 0). Weight, blood pressure and pulse rate will be recorded for all patients in line with study SOPs. The patient will also complete questionnaires to provide demographic and medical history details and additional data will be collected. Participants will be counselled about the study visits and provided with a food diary to record their food intake during the week. Participants will each receive support from the dieticians and weight management practitioners and/or clinicians with regards to maintaining reduced calorie intake according to their respective groups. Participants may contact their study team or GP at any time.

Eligible participants will then be randomly assigned to one of two groups in a 1:1 ratio:

- 1) The *control group* (SC) – standard care including diet, exercise and behaviour modification therapy. Energy expenditure information (RMR, RQ) measured from IC will be **withheld** from participants until the final visit. Participants will receive a standard nutritional energy goal based on the Harris-Benedict equation, the standard predictive equation used at Tier 3 weight management service at Aintree University

Hospital. Both participants and the study clinician providing advice and care will be “blinded” to the client and practitioner report until the completion of the final visit (week 24). To maintain the “blinding” of both participant and clinician in the SC group, the IC measurement is performed and an electronic copy of this is stored in the database, without showing the report to the participant or clinician. Upon completion of the final visit, SC group participants will be able to request a copy of the relevant client reports, should they wish to do so.

- 2) The *intervention group* (ECAL) – diet, exercise, and behaviour modification therapy, with the addition of a personalised nutrition energy goal based on the RMR measured from the IC at every visit. ECAL group participants will receive a client report which is a layperson summary of their personalised RMR, fat burning (%) and glucose availability (%) in a client report printout. The client report is generated directly from the ECAL indirect calorimeter using the ECHealth software contained within. Layperson summary is simplified, easy to understand and has graphic representations of their personalised measurements. The participants will be given one copy of this client printout after each IC measurement. On the other hand, the clinician will receive a practitioner report, a different version to the client printout, also generated from the ECHealth software, which contains the clinical results. The clinician will make recommendations of dietary modification and physical activity counselling based on the clinical results of measured RMR and RQ.

All participants will receive diet and physical activity counselling and provided with a food diary to record their food intake (at least 4 days during the week). Support will be offered from the dieticians and weight management practitioners and clinicians with regards to maintaining a low-calorie intake. Compliance and adherence to dietary plan will be assessed by the dietician or weight management practitioner or clinician review during appropriate study visits with diet and physical activity counselling. A discussion about patient’s food intake will be carried out and documented alongside self-reported food intakes based on their food diary completion.

5.3 Randomisation

During the baseline visit (week 0), randomisation will be conducted through a validated online system provided through the Clinical Trials Unit. Eligible participants will be randomly assigned in a 1:1 ratio to:

- 1) SC (control group) – standard care including diet, exercise and behaviour modification therapy, but energy expenditure information is **withheld** from both the clinicians and participants until the final visit.
- 2) ECAL (intervention group) – in addition to diet, exercise and behaviour modification therapy, participants will receive verbal feedback on nutrition energy goal based on their REE measurement. The REE information will then be used to guide dietary and lifestyle recommendations. The measured energy information will be presented to the participant as a layperson summary at respective visits. This includes RMR, RQ and any other metabolic measurements obtained from IC tests.

Participants will be informed of their randomization assignment during the Baseline Visit. A letter will be sent to the participant's GP notifying them of their patient's participation in the study.

5.4 Standard Care Group Clinical Visits

(weeks 1, 2, 4, 8, 12, 16, 20 and 24)

Standard Care (SC) group participants will receive IC testing at baseline (week 0), week 1, 2, 4, 8, 12, 16, 20 and week 24, but energy expenditure information is **withheld** from the patient until the final visit. Participants would receive a standard nutritional energy goal based on standard predictive equations. At the final visit (week 24), a summary of their energy expenditure (RMR, RQ) information will be provided and presented as a layperson print out.

SC group participants will continue to receive diet, exercise and behavior modification therapy as a standard multicomponent weight management intervention as part of their weight management service.

5.5 - ECAL Group Clinical Visits

(week 1, 2, 4, 8, 12, 16, 20 and 24)

In addition to the multicomponent weight management intervention (diet, exercise and behavior modification therapy), ECAL group participants will receive energy expenditure information measured from IC.

ECAL group participants will receive IC testing at baseline (week 0), week 1, 2, 4, 8, 12, 16, 20 and week 24. RMR measured from IC test will be proven to be more accurate and less variable than standard predictive equations. REE will provide the basis of specific caloric restriction necessary for the individual to maintain their target weight loss. RQ will also be generated from the ratio of VCO_2/VO_2 which provides information about substrate oxidation, more specifically measured fat utilization over the past 24 hours. REE and RQ

information will be used to guide clinicians in recommending the appropriate caloric restriction and lifestyle changes to help promote active weight loss. Participants will receive verbal feedback and a layperson summary of the recommendations. The indirect calorimetry can also be used to demonstrate and compare the results of REE and RQ from previous weeks.

5.6 Control & Intervention Group

- 1) *Control group* – SC Group. Standard care including multicomponent weight management intervention (diet, exercise and behaviour modification therapy) **but** energy expenditure information is **withheld** from both the clinicians and participants until the final visit.
- 2) *Intervention group* - ECAL Group. In addition to standard care, participants will receive verbal feedback on nutrition energy goal based on their REE measurement. The REE information will then be used to guide dietary and lifestyle changes. The measured energy information will be presented as a layperson summary at respective visits. This includes RMR, RQ and any other metabolic measurements obtained from IC tests.

5.7 Neuropathy screening questionnaires

(weeks 0, 4, 12 and 24)

All the participants will be offered 3 neuropathy screening questionnaires DN4, mTCNS, BPI-SF and a visual analogue scale (VAS) of neuropathic pain at week 0 (baseline), 4, 12 and week 24. These questionnaires are anticipated to take no longer than 10 minutes to complete.

5.8 Vibration Perception Threshold & Neurothesiometry

(weeks 0, 4, 12 and 24)

For measuring quantitative vibration perception threshold (VPT) a Neurothesiometer (Horwell, Scientific Laboratory Supplies, Wilford and Nottingham, UK) will be used.

Procedure for Neurothesiometer

The patient should be in a semi-recumbent position, with heels resting on the bed. Prior to the testing, patient will be familiarized with the sensation of vibration at the wrist. The probe is then balanced on the tip of the great toe (right and left). The amplitude of the vibration for the probe should be increased from zero, by turning the Neurothesiometer dial slowly, during which patient's eyes are shut. Participants will be instructed to say "yes" when he/she first

detects the slightest “buzzing” or vibration sensation, and this is recorded as the vibration perception threshold which is repeated three times on each test site. The unit of VPT is in volts and has a range between 0-50 volts. A grading scale which can be used is: no neuropathy (VPT < 15V), mild neuropathy (VPT < 25V), moderate neuropathy (25-35V), severe neuropathy (VPT > 35V).

